8.6 Laboratory Unit Conversion

Since more than one clinical laboratory will be used as a source for laboratory test results, an evaluation will be done to compare the units for each laboratory test and where units differ, the units will be converted to a standard unit and the conversion factors will be provided in analysis data model (ADaM) specifications.

9 ANALYSIS SETS

The following population will be used for safety analyses:

- Safety set
All patients who are randomized and take at least 1 dose of study drug. Treatment assignment will be based on the treatment actually received.

The following populations will be used for efficacy analyses:

- Intention-to-Treat (ITT) set
All patients who are randomized to study. Treatment assignment will be based on the randomized treatment.
- Modified Intention-to-Treat (mITT) set
All patients who take at least one dose of study drug and have at least one follow-up efficacy or biomarker outcome evaluation. Treatment assignment will be based on the randomized treatment.
- Per Protocol (PP) set
All patients who take at least one dose of study drug and do not have an important major protocol deviation. Treatment assignment will be based on the treatment actually received.

10 STUDY POPULATION

10.1 Patient Disposition

Patient disposition will be summarized as follows:

- The number of patients screened, the number of randomized patients, and number of patients in each analysis set will be summarized by treatment group and total.

- The number of patients randomized but not treated, completed the study drug, the reason for discontinuation of study drug, the number of patients completed the study, and the reason for discontinuation of study will be summarized by treatment group and total.

Additionally, the number of patients per site will be tabulated.

Patients excluded from the analysis sets and the reason for their exclusion will be listed in Appendix of the CSR.

The possible reasons for exclusion from the analysis sets are provided in the below table.

Table 10.1.1 Reason for Exclusion from Analysis Sets

Analysis Set	Reason for exclusion
ITT set	- Patient was not randomized to the study drug
Safety set	- Patient who did not take at least 1 dose of study drug
mITT set	- Patient who did not take at least 1 dose of study drug - Patient who did not have at least one follow-up outcome evaluation
PP set	- Patient who did not take at least 1 dose of study drug - Patient who had important major protocol deviation

Additionally, the number and percentage of patients remaining on the study at each visit will be summarized.

10.2 Screen Failures

Screen failures are defined as patients who consent to participate in the clinical study but are not subsequently randomized. A minimal set of screen failure information is required to ensure transparent reporting of screen failure patients to meet the Consolidated Standards of Reporting Trials (CONSORT) publishing requirements and to respond to queries from regulatory authorities. Minimal information includes demography, screen failure details, eligibility criteria, and any SAEs.

Standard continuous variable summary for the age and categorical variable summaries for sex, ethnicity, race, inclusion criteria not met, and exclusion criteria met will be presented for total number of screen failure patients.

10.3 Protocol Deviations

Major protocol deviations that could potentially affect the safety or preliminary efficacy conclusions of the study will be identified before database lock and unblinding of individual patient treatment information. Details about protocol deviations can be found in the protocol deviation plan.

All protocol deviations, including the deviation designation (major or minor) and category will be presented in Appendix of the CSR.

10.4 Demographic and Baseline Characteristics

Standard continuous or categorical variable summaries will be presented by treatment group and total for the following variables based on the safety set.

- Age at informed consent (years)
- Age group (< 60 years, \geq 60 years; sub categories: 60 – 69, 70 -79, \geq 80)
- Sex
- Ethnicity
- Race
- Height at screening (cm)
- Weight at screening (kg)
- Body mass index (BMI) at screening (kg/m^2)
- BMI group ($< 30 \text{ kg}/\text{m}^2$, $\geq 30 \text{ kg}/\text{m}^2$)
- Female of childbearing potential
- Dexamethasone use at time of randomization
- Remdesivir use at time of randomization

Where more than one race category has been selected for a subject, these race categories will be combined into a single category labeled “Multiple Race” in the summary tables. The listings will reflect the original selected categories.

10.5 Medical History

The verbatim term of the medical history (including smoking, drug, and alcohol use/abuse history) condition/event will be coded using the Medical Dictionary for Regulatory Activities (MedDRA), Version 23.0 or above.

Separate listings of medical history and COVID-19 related medical history will be presented for the safety set.

10.6 Prior and Concomitant Medications

Prior and concomitant medication verbatim terms in the eCRFs will be mapped to Anatomical Therapeutic Chemical (ATC) class and preferred names using the WHODrug global dictionary (Version September, 2020) or above.

Prior medications are those medications that started and stopped before the initial dose of study drug. Concomitant medications are those medications that started after the initial dose of study drug or medications that started before the initial dose of study drug and continued during the treatment period.

Prior and concomitant medications will be summarized for each treatment by WHO ATC class and preferred term (PT). These summaries will present the number and percentage of patients

using each medication. Patients may have more than 1 medication per ATC class and PT. At each level of patient summarization, a patient is counted once if he/she reported 1 or more medications at that level. Each summary will be ordered by descending patient count in the total column by ATC level and PT. Additional summary will be provided for concomitant COVID-19 medications.

The safety set will be used to summarize medication data.

11 SAFETY ANALYSES

All safety analyses will be presented for the safety set.

11.1 Extent of Exposure

All patients are to receive 1 tablet, 3 times daily for 14 days. To fit into the clinical practice of treating patients with severe COVID-19, screening visit and baseline visit can be combined in some patients. In that case, the number of dosing could be less than 3 times on that day. Patients discharged from the hospital prior to Day 14 will not take any study drug after discharge.

The extent of exposure to study drug will be examined by assessing the total number of tablets received per patient. The total number of tablets taken per patient will be summarized using descriptive statistics by treatment group.

Additionally, the duration of treatment (days) will be calculated as follows:

- Treatment duration (days)=(Date of last administration–Date of first administration) + 1

The treatment duration per patient will be summarized using descriptive statistics by treatment group.

11.2 Adverse Events

Adverse events will be coded to System Organ Class (SOC) and PT using MedDRA (Version 23.0 or above). The coding process is described in the Data Management Plan. Severity of AEs will be graded based on the National Cancer Institute (NCI) Common Terminology Criteria for Adverse Events (CTCAE) Version 5.0.

TEAEs are defined as those AEs that occurred after dosing and those existing AEs that worsened during the study. If it cannot be determined whether the AE is treatment emergent due to a partial onset date, then it will be counted as such.

Elevated Alanine transaminase (ALT), Aspartate transaminase (AST), and creatinine levels in plasma are considered as AEs of potential interest. The list of preferred terms for AEs of potential interest are provided in [Appendix 1](#).

TEAEs occurring during the 14-day treatment period will include those with onset in the first 14 days following first treatment date, irrespective of actual days of treatment.

Related AEs are those reported as “Definite,” “Probable,” or “Possible,” and unrelated AEs are those reported as “Unlikely” or “Unrelated”. AEs with a missing relationship are considered related to study drug.

Each AE summary will be displayed by treatment group and total. Summaries that are displayed by SOC and PT will be ordered by descending patient count in the total column by SOC and PT. Summaries of the following types will be presented:

- An overview of TEAEs
- Patient incidence of TEAEs and total number of unique TEAEs by MedDRA SOC and PT
- Patient incidence of TEAEs of potential interest and total number of unique TEAEs of potential interest by MedDRA SOC and PT
- Patient incidence of TEAEs and total number of unique TEAEs occurring with onset \leq 7 days, onset \leq 14 days and onset \leq 28 days of first dose by MedDRA SOC and PT
- Patient incidence of TEAEs occurring with onset \leq 7 days, onset \leq 14 days and onset \leq 28 days of first dose by MedDRA SOC, PT, and highest toxicity grade. At each level of patient summarization, a patient is classified according to the highest toxicity grade if the patient reported 1 or more events. Adverse events with missing toxicity grade will be considered severe for this summary.
- Patient incidence of TEAEs occurring with onset \leq 7 days, onset \leq 14 days and onset \leq 28 days of first dose by MedDRA SOC, PT, and closest relationship to study drug (Definitely Related/ Probably Related/ Possibly Related/ Unlikely Related/ Unrelated). At each level of patient summarization, a patient is classified according to the closest relationship if the patient reported 1 or more events. Adverse events with a missing relationship will be considered definitely related for this summary.
- Patient incidence of drug-related TEAEs occurring with onset \leq 7 days, onset \leq 14 days and onset \leq 28 days of first dose by MedDRA SOC and PT
- Patient incidence of drug-related TEAEs occurring with onset \leq 7 days, onset \leq 14 days and onset \leq 28 days of first dose by MedDRA SOC, PT, and highest toxicity grade
- Patient incidence of treatment-emergent SAEs occurring with onset \leq 7 days, onset \leq 14 days and onset \leq 28 days of first dose by MedDRA SOC and PT
- Patient incidence of TEAEs leading to study drug discontinuation with onset \leq 7 days, onset \leq 14 days and onset \leq 28 days of first dose by MedDRA SOC and PT
- Patient incidence of deaths with onset \leq 7 days, onset \leq 14 days and onset \leq 28 days of first dose by MedDRA SOC and PT
- Listing of SAEs (presented in the Table section of the appendices)

- Listing of AEs resulting in study drug discontinuation (presented in the Table section of the appendices)
- Listing of AEs resulting in death (presented in the Table section of the appendices)

All AEs will be listed. An additional listing of all AEs of potential interest will also be created.

AEs will be analyzed descriptively including 2-sided 95% CI for between-group (SIRI-365 – placebo) incidence rates. Incidence rates among treatment groups will be compared using the Fisher exact test. AEs analyzed will include, but not necessarily limited to following:

- At least 1 AE with onset \leq 7 days of first dose
- At least 1 AE with onset \leq 14 days of first dose
- At least 1 AE with onset \leq 28 days of first dose
- At least 1 TEAE with onset \leq 7 days of first dose
- At least 1 TEAE with onset \leq 14 days of first dose
- At least 1 TEAE with onset \leq 28 days of first dose
- At least 1 Drug-Related TEAE
- At least 1 SAE
- At least 1 TEAE of Severe Intensity
- AE leading to study drug discontinuation
- Death

Additionally, the Exposure Adjusted Incidence Rate (EAIR) of AEs will be summarized by treatment group. The EAIR of AEs is calculated as the number of subjects with an event (preferred term), divided by the total exposure time of all subjects at risk of an initial occurrence of that event. For a subject who never experiences the event, the exposure time is calculated as the duration between the date/time of first study drug administration, to the date of last follow-up assessment (end of study participation). For subjects with at least one occurrence of an event, the exposure time is the duration between the date/time of first study drug administration, to the date/time of the first occurrence of that event.

This will be presented as the number of subjects reporting the event and calculated EAIR in person-weeks.

A similar summary will be provided of the EAIR of related AEs by preferred term.

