**10.3.2. Safety Analysis*****TEAEs***

TEAEs are defined as AEs that commence or worsen after the first dose of study medication during the study. TEAEs will be analyzed descriptively including 2-sided 95% CI for between-group (SIR1-365 – placebo) incidence rates. TEAEs analyzed will include, but not necessarily limited to, the following:

- At least 1 TEAE
- At least 1 Related TEAE
- At least 1 SAE
- At least 1 TEAE of severe intensity
- Individual TEAE Preferred terms

- Individual TEAE Preferred terms considered related to study medication

TEAEs occurring during the 14-day treatment period will include those with onset in the first 14 days, irrespective of actual days of treatment, where study day 1 is the date of the first dose of study medication. All TEAEs with onset  $\leq$  28 days will be summarized similarly.

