#### Follow-up of AE and SAE

- The Investigator is obligated to perform or arrange for the conduct of supplemental measurements and/or evaluations as medically indicated or as requested by sponsor or CRO to elucidate the nature and/or causality of the AE or SAE as fully as possible. This may include additional laboratory tests or investigations, histopathological examinations, or consultation with other health care professionals.

- If a patient dies during participation in the study or during a recognized follow-up period, the Investigator will provide CRO with a copy of any post-mortem findings including histopathology.
- New or updated information will be recorded in the originally completed CRF/ SAE form.
- The Investigator will submit any updated SAE data to CRO within 24 hours of receipt of the information.

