8.2 Standard Calculations

Variables requiring calculations will be derived using the following formulas:

- Baseline: A Baseline value, unless specified otherwise, is the last non-missing value recorded prior to the first dose of study drug.
- Study day: For a given date, study day will be calculated as the number of days from the day of first dosing of study drug, labeled day 1, therefore:

Study day = date of event/measurement - date of first dose of study drug + 1, for events/measurements on or after first dose

Study day = date of event/measurement - date of first dose of study drug, for events/measurements before first dose

- Durations (days): Durations, expressed in days, will be calculated as follows:

Duration in days = (Stop date/time of event – Start date/time of event)/(3660x24)

If the stop or start time is missing, only the date information will be used as follows:

Duration in days = Stop date of event – Start date of event + 1

- Height: Height entries made in inches are converted to centimeters using the following formula:

Height (cm) = Height (in) × 2.54

- Weight: Weight entries made in pounds are converted to kilograms using the following formula:

Weight (kg) = Weight (lb)/2.2046

- Body Mass Index (BMI): BMI is calculated using height and weight and is calculated using the following formula:

BMI (kg/m²) = Weight (kg) / [[Height (cm) / 100]²]

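### SAP 11.2 loosens the protocol's treatment-emergent rule and drops its Day 1 anchor, and both documents use an onset-only window that cannot place pre-dose events that worsen on drug

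*SAP*

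**What the plan says.** **Endpoint.** Protocol section 4 and SAP section 4 agree: the primary measure is the percentage of patients with any TEAE from Baseline to Day 14.

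**Protocol rule (synopsis and section 10.3.2).** "TEAEs are defined as AEs that commence or worsen after the first dose of study medication during the study". For the 14-day period the protocol takes events with "onset in the first 14 days, irrespective of actual days of treatment, where study day 1 is the date of the first dose". The 28-day summary is also selected by onset.

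**SAP rule (section 11.2).** "TEAEs are defined as those AEs that occurred after dosing and those existing AEs that worsened during the study". The 14-day period covers "those with onset in the first 14 days following first treatment date, irrespective of actual days of treatment". The list of comparisons later in the same section uses a third form, onset no more than 7, 14 or 28 days from first dose, and gives no lower limit.

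**Study day (SAP section 8.2).** For dates on or after first dosing, "Study day = date of event/measurement - date of first dose of study drug + 1".

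**Collection and updates.** Protocol section 8.2.2.1 starts adverse event collection when consent is signed, and screening may last up to 7 days. On follow-up, Protocol Appendix 4 says: "New or updated information will be recorded in the originally completed CRF/ SAE form".

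**Declared changes.** SAP section 15 states that there are none.

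**The concern.** The two documents give different rules for the one primary endpoint, and the SAP does not acknowledge the difference. The protocol ties both the start and the worsening of an event to the first dose. The SAP ties only new events to dosing and ties worsening to the study as a whole, which includes screening. The window sentence has also lost the statement that Day 1 is the date of first dose.

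A second problem lies in both documents. TEAEs include worsened pre-existing events, but the 14-day period is filled by onset date, and neither document says which date a worsened event carries. A programmer working from this text could build the primary endpoint in several ways, with different patient counts. If that is noticed after unblinding, the choice is made with treatment known.

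**Working it through.** The plan has no figure to reproduce. It gives no TEAE rate, and SAP section 6 says the 30 patients per group do not come from a significance calculation. The check therefore compares the texts and applies date arithmetic.

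**Step 1: the definitions.** Take an event that begins after consent and worsens only before the first dose. It does not start or worsen after first dose, so it is not a TEAE under the protocol. It is an existing event that worsened during the study, so read literally it is a TEAE under the SAP. It therefore enters every SAP table of TEAEs without a time window, such as the TEAE overview.

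**Step 2: the window.** Under SAP 8.2, the first-dose date + 13 days is study Day 13 + 1 = 14, and the first-dose date + 14 days is study Day 14 + 1 = 15.

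| Onset relative to first-dose date | Study day | Protocol, Days 1-14 | SAP, first-dose date to +14 | SAP, strictly after first-dose date, to +14 | SAP list, 14 elapsed days, no lower bound | SAP list, study day ≤ 14, no lower bound |
|---|---|---|---|---|---|---|
| -3 days | -3 | out | out | out | in | in |
| 0 | 1 | in | in | out | in | in |
| +13 days | 14 | in | in | in | in | in |
| +14 days | 15 | out | in | in | in | out |

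The SAP wording can thus admit Day 15, and its strictest reading would drop Day 1. Pre-dose onsets enter only where no lower bound is applied. The SAP lists any AE and any TEAE as separate comparisons for the same onset limit. With a bound at the first-dose date, these could differ only through pre-dose events on Day 1. That hints at no lower bound but does not establish it.

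**Step 3: size of a fifteenth day.** Assume a constant hazard, so P15 = 1 - (1 - P14)^(15/14). The 14-day rates P14 are assumptions.

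| P14 | P15 | Difference (points) | Patients per arm of 30 |
|---|---|---|---|
| 30% | 31.8% | 1.76 | 0.53 |
| 50% | 52.4% | 2.42 | 0.72 |
| 60% | 62.5% | 2.53 | 0.76 |
| 70% | 72.5% | 2.47 | 0.74 |
| 80% | 82.2% | 2.17 | 0.65 |
| 90% | 91.5% | 1.52 | 0.45 |

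**Step 4: a pre-dose event that worsens.** Suppose the record keeps an onset of study Day -3.

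| First worsening | TEAE, protocol | TEAE, SAP | 14-day count if onset must be Day 1 or later | SAP 14-day count if no lower bound | TEAE by protocol definition, dated by worsening, within Days 1-14 |
|---|---|---|---|---|---|
| Day -1 only | no | yes | out | in | no |
| Day 7 | yes | yes | out | in | yes |
| Day 25 | yes | yes | out | in | no |

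With a lower bound, the Day 7 case is lost, and the protocol's own Day 1-14 onset rule loses it too. Without one, all three count whatever the date of worsening. Neither reading reproduces the last column.

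**Step 5: weight of one patient.** A patient whose classification changes moves a 30-patient arm by 1/30 = 3.3 percentage points. This happens only if the patient has no other qualifying TEAE.

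**The case against.** The sponsor can fairly answer as follows.

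- **Intent.** SAP section 4 says Baseline to Day 14, section 8.2 labels the first dosing day as Day 1, and section 15 declares no changes. Together they suggest that the protocol meaning was intended. This stands, and it makes Day 15 an ambiguity and not a stated rule. A strict count of 14 days after the first-dose date gives Days 2-15, still 14 days. The window becomes longer only if the first-dose date is also included.
- **Reach.** The endpoint is any TEAE per patient, so many misclassified events would change nothing. Some patients have screening and baseline combined, which shortens the pre-dose period. Both points stand.
- **Records.** The Appendix 4 sentence on updating the original form sits among instructions on supplemental evaluations, post-mortem findings and SAE updates. It does not establish that a worsened event keeps its first onset date. Appendix 4 also lists exacerbation of a pre-existing condition as an event in its own right, which favours a separate record. The annotated eCRF and Data Management Plan, cited in SAP section 2, may settle this, but they are not available here.

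A reader might infer that the SAP departs from the protocol in a way that makes it miss pre-dose events that worsen on drug. The documents do not support that. The SAP expressly includes worsened existing events, and the protocol fills its 14-day period by onset in the same way. Any loss is common to both. Nor can the primary count both admit screening-only worsening and lose on-drug worsening, because the first needs no lower bound on onset and the second needs one.

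These answers do not remove the difference between worsening during the study and worsening after the first dose, or the absence of a dating rule for worsened events.

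**Conclusion.** The point holds within limits, at minor to moderate severity.

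- **Definition.** The SAP's treatment-emergent rule is looser than the protocol's, and the difference is undeclared. It affects TEAE summaries without a window. It reaches the primary count only if the SAP's onset limit has no lower bound.
- **Window.** The SAP text can be read to admit study Day 15. The effect is 1.5 to 2.5 percentage points, or 0.45 to 0.76 patients per arm of 30, assuming a constant hazard and 14-day rates of 30% to 90%.
- **Shared gap.** An onset-only window in both documents either drops a pre-dose event that worsens on drug or counts it regardless of when it worsened. This assumes that the worsening has no dated record of its own.

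The number of patients affected cannot be derived from the documents. The reason to act is an unresolved definition of the primary endpoint, not evidence of a large bias.

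**What to change.** 1. In SAP 11.2, restore the protocol definition: the event must start or worsen after the first dose.
2. In SAP 11.2, define the primary window as study Days 1-14 by the section 8.2 formula, with Day 1 the first-dose date. Define the other windows as Days 1-7 and 1-28, and use this one form throughout the section.
3. In both documents, state that a pre-dose event that worsens is placed in a window by the date of its first worsening after the first dose.
4. Confirm that the eCRF captures that date. If it does not, instruct sites to enter a post-dose worsening as a new record.
5. If the sponsor means to keep the current SAP wording, list the difference in SAP section 15.

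The cost is a few sentences in the SAP, one in the protocol and, if needed, a line in the eCRF completion guide. It should be done before unblinding.
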